3.9.1.1. Liver Chemistry Follow-up Procedures

Refer to the diagram in [Appendix 8](#) for a visual presentation of the procedures listed below.

The procedures listed below are to be followed if a subject meets the liver chemistry stopping criteria defined in Section 3.9.1:

- Immediately and permanently withdraw the subject from study treatment
- Notify the GSK Medical Monitor within 24 hours of learning of the abnormality to confirm the subject's study treatment(s) cessation and follow-up
- Complete the "Safety Follow-Up Procedures" listed below
- Complete the liver event electronic case report forms (eCRFs). If the event also meets the criteria of a serious adverse event (SAE) (see Section 8.2), the SAE data collection tool will be completed separately with the relevant details
- Upon completion of the safety follow-up permanently withdraw the subject from the study and do not rechallenge with study treatment(s)

Safety Follow-Up Procedures for subjects with ALT ≥ 3 times ULN:

- Monitor subjects **weekly** until liver chemistries (ALT, aspartate aminotransferase [AST], alkaline phosphatase [ALP], and bilirubin) resolve, stabilize or return to within baseline values

Safety Follow-Up Procedures for subjects with ALT ≥ 3 times ULN and bilirubin ≥ 2 times ULN (or ALT ≥ 3 times ULN and INR > 1.5):

- **This event is considered an SAE** (see Section 8.2). Serum bilirubin fractionation should be performed.
- Make every reasonable attempt to have subjects return to the clinic within 24 hours for repeat liver chemistries, additional testing, and close monitoring (with specialist or hepatology consultation recommended)
- Monitor subjects **twice weekly** until liver chemistries (ALT, AST, alkaline phosphatase, bilirubin) resolve, stabilize or return to within baseline values

In addition, for all subjects with ALT ≥ 3 times ULN, every attempt must be made to also obtain the following:

- Viral hepatitis serology including:
 - Hepatitis A Immunoglobulin M (IgM) antibody
 - Hepatitis B surface antigen and Hepatitis B Core Antibody (IgM)
 - Hepatitis C ribonucleic acid (RNA)
 - Cytomegalovirus IgM antibody
 - Epstein-Barr viral capsid antigen IgM antibody (or if unavailable, obtain heterophile antibody or monospot testing)
 - Hepatitis E IgM antibody (if subject resides outside the United States (US) or Canada, or has traveled outside US or Canada in past 3 months)

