6.3. Permanent Discontinuation from Study Treatment

Subjects will receive study treatment until disease progression, death or unacceptable toxicity, including meeting stopping criteria for significant toxicity as outlined in Section 3.10 and other relevant safety management guidelines outlined in the protocol, or until a maximum of 16 treatment cycles. In addition, study treatment may be permanently discontinued for any of the following reasons:

- deviation(s) from the protocol
- request of the subject or proxy (withdrawal of consent by subject or proxy)
- investigator's discretion
- a dose delay of >14 days unless the investigator or GSK Medical Monitor agree that subject derives benefit and that further treatment benefits will outweigh the risks. Exceptions apply to nephrotoxicity as outlined in Section 3.10.2
- intercurrent illness that prevents further administration of study treatment(s)
- subject is lost to follow-up
- study is closed or terminated
- subject completes maximum number of treatment cycles per protocol
- The primary reason study treatment was permanently discontinued must be documented in the subject's medical records and electronic case report form (eCRF)

If the subject voluntarily discontinues from treatment due to toxicity, 'adverse event (AE)' will be recorded as the primary reason for permanent discontinuation on the eCRF.

Once a subject has permanently discontinued from study treatment, the subject will not be allowed to be retreated.

All subjects who discontinue from study treatment will have safety assessments at the time of discontinuation and during post-study treatment follow-up as specified in Time and Events Tables (see Section 7.1).

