9. LIVER CHEMISTRY FOLLOW-UP PROCEDURES

9.1. Liver Chemistry Testing Procedures

For subjects meeting any of the liver chemistry stopping criteria in Section 3.9.1, make every attempt to carry out the **liver event follow-up assessments** described below:

- Viral hepatitis serology, including:
 - Hepatitis A IgM antibody
 - Hepatitis B surface antigen and Hepatitis B Core Antibody (IgM)
 - Hepatitis C RNA
 - Cytomegalovirus IgM antibody
 - Epstein-Barr viral capsid antigen IgM antibody (or if unavailable, then obtain heterophile antibody or monospot testing)
- Blood sample for pharmacokinetic (PK) analysis. Record the date and time of the PK blood sample draw and the date and time of the last dose of study drug prior the blood sample draw on the eCRF. If the date or time of the last dose is unclear, provide the subject's best approximation. If the date or time of the last dose cannot be approximated, or if a PK sample cannot be collected within 48 hours of the liver chemistry event, do not obtain a PK sample. Instructions for sample handling and shipping are found in the Study Procedures Manual (SPM).
- Serum creatinine phosphokinase (CPK) and lactate dehydrogenase (LDH)

- Fractionate bilirubin, if total bilirubin ≥ 2 X upper limit of normal (ULN)
- Obtain a complete blood count (CBC) with differential to assess eosinophilia
- Record the appearance or worsening of clinical symptoms indicative of hepatitis or hypersensitivity, such as fatigue, nausea, vomiting, right upper quadrant pain or tenderness, fever, rash or eosinophilia as relevant on the AE eCRF
- Record the use of concomitant medications, including acetaminophen, herbal remedies or any other over the counter (OTC) medications, or any putative hepatotoxins, on the concomitant medication eCRF
- Record alcohol use on the liver event alcohol intake eCRF

The following assessments are required for subjects with ALT ≥ 3 X ULN and bilirubin ≥ 2 X ULN (>35% direct) but are optional for other abnormal liver chemistries:

- Anti-nuclear antibody, anti-smooth muscle antibody, and Type 1 anti-liver kidney microsomal antibodies
- Liver imaging (ultrasound, magnetic resonance imaging [MRI] or computed tomography [CT]) to evaluate liver disease

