9.3. Drug Restart/Rechallenge Following Liver Events that are Possibly Related to Study Drug

Approval by the GSK Medical Monitor to restart/rechallenge study drug may be considered where:

- The subject is receiving compelling benefit, the benefit exceeds the risk, and no effective alternative therapy is available. Approval of restart/rechallenge by the Institutional Review Board (IRB) or Independent Ethics Committee (IEC) must be obtained, as required

- If the restart/rechallenge is approved by GSK in writing, then the subject must be provided with a clear description of the possible benefits and risks of administration of study drug, including the possibility of a recurrence, a more severe liver injury or death.
- The subject must also provide signed informed consent specifically for the study drug restart/rechallenge. Documentation of the informed consent must be recorded in the subject's study chart.
- Study drug must be administered at the dose specified by the GSK Medical Monitor.
- Subjects approved by GSK for restart/rechallenge of study drug must return to the clinic twice a week for evaluation of liver chemistry tests until stable liver chemistries have been demonstrated and laboratory monitoring may resume per protocol.

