9.4. Drug Restart Following Transient, Resolving Liver Events Not Related to Study Drug

Approval by the GSK Medical Monitor to restart study drug(s) may be considered where:

- Liver chemistry abnormalities have a clear underlying cause (e.g., biliary obstruction, hypotension) and liver chemistries have improved to normal or are within 1.5 X baseline and ALT <3X ULN. Approval of restart by the Institutional Review Board (IRB) or Independent Ethics Committee (IEC) may be required.
- If the restart/rechallenge is approved by GSK in writing, then the subject must be provided with a clear description of the possible benefits and risks of administration of study drug(s), including the possibility of a recurrence, a more severe liver injury or death.
- The subject must also provide signed informed consent specifically for the study drug(s) restart/rechallenge. Documentation of the informed consent must be recorded in the subject's study chart.
- Study drug(s) must be administered at the dose specified by the GSK Medical Monitor.
- Subjects approved by GSK for restart/rechallenge of study drug(s) must return to the clinic once a week for evaluation of liver chemistry tests until stable liver chemistries have been demonstrated and laboratory monitoring may resume per protocol.
- If protocol-defined stopping criteria for liver chemistry abnormalities are met, study drug(s) administration must stop.

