16.7. Appendix 8: Liver Safety Drug Restart Guidelines

Drug restart may be considered for a subject exhibiting compelling benefit for a critical medicine following drug-induced liver injury, if there is favorable benefit: risk ratio and no alternative medicine available.

Background Information on Drug Restart/Rechallenge

Following drug-induced liver injury, **drug restart or rechallenge is associated with a 13% mortality across all drugs in prospective studies.**¹ Clinical outcomes vary by drug, with nearly 50% fatality with halothane readministered in one month of initial injury. However, some drugs seldom result in recurrent liver injury or fatality. Risk factors for a fatal drug restart/rechallenge outcome include: hypersensitivity¹ with initial liver injury (e.g. fever, rash, eosinophilia), jaundice or bilirubin $\geq 2 \times \text{ULN}$ or $\text{INR} > 1.5$ suggesting severe liver injury, prior IP-related severe or fatal drug restart/rechallenge^{2,3} or evidence of drug-related preclinical liability / mitochondrial impairment³.

Drug Restart/Rechallenge Process (also see [Figure 1](#))

6. Principal Investigator (PI) requests consideration of drug restart for a subject receiving compelling benefit from a critical or life-saving drug, who exhibits liver chemistry elevation meeting subject stopping criteria, with no alternative treatment.

GSK Medical Monitor & Clinical Safety Physician to review the subject's restart/rechallenge risk factors & complete checklist ([Table 18](#)).

[figure not shown]
Table 18 Checklist for drug restart/rechallenge for critical medicine

(Following drug-induced liver injury, drug rechallenge is associated with 13% mortality across all drugs in prospective studies)		
	Yes	No
Compelling benefit of the investigational product (IP) for this subject and no alternative therapy. Provide brief explanation:		
Relative benefit-risk favorable for drug restart/rechallenge , after considering the following high risk factors:		
• Initial liver injury event included:		
– fever, rash, eosinophilia, or hypersensitivity		
– or bilirubin $\geq 2 \times \text{ULN}$ (direct bilirubin $> 35\%$ of total)		
• Subject currently exhibits ALT $\geq 3 \times \text{ULN}$, bilirubin $\geq 2 \times \text{ULN}$ (direct bilirubin $> 35\%$ of total), or INR ≥ 1.5		
• Severe or fatal restart/rechallenge has earlier been observed with IP If yes, please provide brief explanation:		

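### The protocol both forbids and permits rechallenge after a liver stopping event, so a safety stopping rule has two opposite consequences for the same subject

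*Protocol*

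**What the plan says.** Two groups of passages in the protocol deal with a subject whose liver chemistry meets a stopping criterion.

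**Withdrawal without return**
- Section 3.9.1.1 sets its scope: "The procedures listed below are to be followed if a subject meets the liver chemistry stopping criteria defined in Section 3.9.1". Its first instruction is "Immediately and permanently withdraw the subject from study treatment" and its last is "Upon completion of the safety follow-up permanently withdraw the subject from the study and do not rechallenge with study treatment(s". It states no exception.
- Section 6.3 states a general rule: "Once a subject has permanently discontinued from study treatment, the subject will not be allowed to be retreated".
- Section 1.3.1 gives withdrawal from the study as the hepatotoxicity mitigation for subjects meeting these criteria.
- Section 3.3.3 lists liver toxicity meeting the stopping criteria as a DLT. It lets a subject with a DLT remain on study only where the toxicity did not meet stopping criteria.

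**Conditional return to treatment**
- Section 9.3, for liver events possibly related to study drug: "Approval by the GSK Medical Monitor to restart/rechallenge study drug may be considered where". The conditions include compelling benefit, no effective alternative, written sponsor approval and a specific consent.
- Section 9.4, for events not related to study drug: "Approval by the GSK Medical Monitor to restart study drug(s) may be considered where". Its conditions include a clear underlying cause and recovery of the liver tests.
- Appendix 8 gives a restart process and checklist, and describes the candidate as a subject whose liver chemistry met the stopping criteria.

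**The concern.** A stopping rule should tell every site the same thing about the same patient. Under Section 3.9.1.1 a subject who meets a liver criterion is finished with treatment and, after safety follow-up, with the study. Under Section 9.3 and Appendix 8 the investigator may ask to restart that subject. A rechallenge approved under one part of the protocol would breach two other parts.

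The sponsor plainly regards the decision as grave. Appendix 8 warns that "drug restart or rechallenge is associated with a 13% mortality across all drugs in prospective studies".

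There is also a smaller analysis consequence. Section 13.7 includes data up to study completion or withdrawal from the study, so the choice of rule fixes how long the subject contributes exposure, safety and response data. Section 13.4.1 makes permanent discontinuation one of the routes into the Evaluable (MM) population used for futility. Section 13.7.2.2 summarises adverse events leading to discontinuation separately. Each depends on whether the subject has permanently stopped.

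**Working it through.** No arithmetic applies. The question is whether the two groups of passages address the same subjects, and whether anything in the text subordinates one to the other.

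**1. Are they the same subjects?**
- Section 3.9.1.1 covers anyone meeting any of the five criteria in Section 3.9.1.
- Appendix 8 names as its candidate a subject whose elevation met the stopping criteria. The overlap is explicit.
- Section 9.1 opens Section 9 with the same group: "For subjects meeting any of the liver chemistry stopping criteria in Section 3.9.1, make every attempt to carry out the", followed by the liver follow-up assessments.
- Section 9.2 handles subjects below the criteria. They continue drug under weekly monitoring, so they have nothing to restart. If one of them later meets any of criteria 1 to 5, Section 9.2 sends the site to the procedures of Section 9, which contains 9.3 and 9.4.

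Sections 9.3 and 9.4 therefore reach subjects who have met the stopping criteria, as Appendix 8 does.

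**2. Is one text written as an exception to the other?**
- Section 3.9.1.1 does not mention 9.3 or 9.4. It refers to Appendix 8 only for a diagram of its own procedures, which are the ones that end in no rechallenge.
- Sections 9.3 and 9.4 do not mention 3.9.1.1 or 6.3.
- No precedence clause was found.
- Where the protocol intends exceptions it writes them in: Section 6.3 carves out nephrotoxicity from its dose-delay rule, and Table 13 lists exceptions by grade.

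**3. Side by side, for one subject who meets a liver criterion**

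| Question | 3.9.1.1, 6.3 and 1.3.1 | 9.3, 9.4 and Appendix 8 |
|---|---|---|
| Treatment | Permanently stopped | Stopped; restart may be approved |
| Rechallenge | Prohibited | Possible with approval and consent |
| Study participation | Ends after safety follow-up | Continues if restarted |

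**4. Section 3.3.3.** In Part 1, meeting the liver criteria in the DLT window (21 or 28 days) is a DLT that by definition met stopping criteria, so the condition for staying on study fails. A restart under 9.3 would conflict with this as well.

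**5. What moves in the analysis.** The response-rate denominator does not: Section 13.7.1 uses the All Treated population, and Section 13.7.7 counts unknown or missing responses as non-responses. Duration of exposure, discontinuation status, any response first seen after a restart, and entry to the Evaluable (MM) population through discontinuation can move.

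**The case against.** The strongest reply is that this is a default rule with a tightly guarded exception, and that little turns on it.

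- **Scope.** Only Appendix 8 names the stopping criteria as its entry condition. Section 9.3 speaks of liver events generally and 9.4 of abnormalities with a clear cause. Doses can also be held without a stopping criterion being met, as for isolated INR elevation in Section 3.10.2. The overlap is less explicit for 9.3 and weakest for 9.4. This does not remove the conflict: Section 9.1 and the referral in 9.2 bring stopping-criteria subjects into Section 9, and Appendix 8 alone is enough to contradict 3.9.1.1.
- **Section 3.3.3.** It goes on to allow a longer recovery time where benefit is shown and the investigator and medical monitor agree. On the natural reading that relaxes the 14-day recovery limit, not the requirement that stopping criteria were not met. It remains a Part 1 rule only.
- **Size.** This point largely stands. Nobody is restarted without sponsor approval, ethics review as required and separate consent; for everyone else both texts lead to stopping.
- **The mortality figure.** This stands too. The 13% is background across all drugs, and Appendix 8 adds that some drugs seldom cause recurrence. It does not measure risk in this trial, and it does not bear on the unrelated events of 9.4.
- **Missing figures.** The Appendix 8 diagrams are not shown and might present restart as an exception. The written text would still contradict itself.

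**Conclusion.** The concern holds. The protocol gives opposite consequences for a subject who meets a liver stopping criterion: permanent withdrawal with rechallenge prohibited, or possible restart by approval. The thresholds in Section 3.9.1 are not in dispute, only what follows from meeting them.

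All five criteria lead into the conflict, but the practical reach is limited to subjects who satisfy every restart condition. The protocol gives no liver-event rate from which to count them; the number is probably small, and the statistical effect is secondary. The point still needs fixing before the protocol is relied on, because two sites following it faithfully could manage the same patient in opposite ways, in a first-in-human study with liver-enzyme elevations in both animal species (Section 1.3.1).

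The conclusion rests on the current written text and assumes that no undisplayed figure supplies a precedence rule. It takes no view on which rule is clinically right.

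**What to change.** Reconcile Sections 1.3.1, 3.3.3, 3.9.1.1, 6.3, 9.3, 9.4 and Appendix 8 so that a single rule on restart after a liver stopping event applies throughout. The sponsor's clinical team must decide what the rule is. Whatever it is, it should be stated once, any exception should be cross-referenced from every section that states the default, and text that no longer applies should be removed. The same amendment should say when such a subject counts as permanently discontinued, so that the Evaluable (MM) definition in Section 13.4.1 and the discontinuation summaries in Section 13.7.2.2 follow without judgement.

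The change is to wording only: sample size, visit schedule and data collection are untouched. It does need a protocol amendment, with the usual approvals in Canada, the United Kingdom and the United States.

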3.9.2. QTc Stopping Criteria

Study treatment will be withheld in a subject who meets the corrected QT (QTc)¹ interval duration criteria below.

- QT interval corrected for heart rate by Fridericia's formula (QTcF) >500 msec
- or

- Increase in QTc of > 60 msec from baseline

¹Based on average QTc value of triplicate electrocardiograms (ECGs) to include manual over-read. For example, if an ECG demonstrates a prolonged QT interval, obtain 2 additional ECGs over a brief period (e.g., within approximately 10 minutes of the abnormal ECG, if possible, and approximately 10 minutes apart from each other), and then use the averaged QTc values of the 3 ECGs to determine whether the subjects should have study treatment withheld.

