3.9.3. Troponin Evaluation and Stopping Criteria

If post-screening, the local cTn is >Institutional ULN it is recommended that subjects undergo urgent evaluation of cardiac ischemia symptoms and ECG should be performed to rule out cardiac ischemia. An urgent repeat of cTn value and collection of sample for central lab evaluation should be obtained within 24 hours.

Asymptomatic subject:

If the second value of cTn is \leq ULN the subject can continue on study with close follow up of symptoms, ECG, and further cTn measurements as clinically indicated

If the second value of cTn remains >ULN treatment with GSK2857916 should be interrupted. The subject should undergo cardiac evaluation including ECHO testing for cardiac function. Any re-start of study treatment must be discussed with the GSK medical monitor who will consult with a member of the internal cardiotoxicity panel prior to re-start.

If the second value of cTn exceeds the threshold for MI according to local lab parameters, obtain cardiology consultation immediately. Permanently discontinue GSK2857916 and withdraw the subject from the study.

Symptomatic subject:

Obtain cardiology consultation immediately. Permanently discontinue GSK2857916 and withdraw the subject from the study.

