3.9.4. Left Ventricular Ejection Fraction (LVEF)

3.9.4.1. LVEF Stopping Criteria

Echocardiography (ECHO) must be performed at Screening and as outlined in the Time and Events Tables (Section 7.1). Subjects who have an asymptomatic, absolute decrease of >15% in LVEF compared with baseline or an absolute decrease of >10% in LVEF compared with baseline and the ejection fraction is below 50% should temporarily interrupt GSK2857916 and have a repeat evaluation of LVEF within 1 week. ECHO should be repeated every 1 to 2 weeks for 4 weeks or until LVEF recovery to within 15% of baseline or to above 50% and within 10% of baseline depending on which stopping criteria above were met.

- If the LVEF recovers (defined as absolute decrease $\leq 15\%$ compared to baseline or $\geq 50\%$ and absolute decrease $\leq 10\%$ compared with baseline) at any time during the next 4 weeks, after consultation and approval of the GSK Medical Monitor, the subject may be restarted on GSK2857916 at a reduced dose. For such subjects, monitoring of LVEF will be performed 2, 4, and 8 weeks after rechallenge, and then per protocol
- If LVEF does not recover within 4 weeks, treatment with GSK2857916 should be permanently discontinued. Ejection fraction should be monitored every 4 weeks for a total of 16 weeks or until resolution

Subjects with Grade 3 or 4 symptomatic left ventricular systolic dysfunction must discontinue treatment with GSK2857916. Ejection fraction should be monitored every 4 weeks for a total of 16 weeks or until resolution.

Copies of all ECHOs and cardiology consultations performed on subjects who experience a $>15\%$ decrease in LVEF from baseline or $>10\%$ decrease in LVEF from baseline and whose cardiac ejection fraction is $<50\%$ will require review by a GSK medical monitor. Instructions for submitting qualifying ECHOs/MUGAs are provided in the SPM.

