3.10.3. Dose Modifications

For GSK2857916 toxicities not specifically addressed in the protocol follow the guidelines outlined in [Table 13](#).

Table 13 Dose Adjustment/Stopping Criteria

Toxicity Grade ^a	Dose Modification of GSK2857916
Grade 1	
 Continue at current dose level. Consider supportive care recommendations
Grade 2	
 If toxicity is considered not clinically relevant, continue with 100% scheduled dose If toxicity is considered clinically relevant withhold the dose until toxicity resolves to Grade 1 or baseline. If resolved within 14 days, then restart at current dose level. Consider supportive care recommendations If not resolved within 14 days, discuss with GSK Medical Monitor
Grade 3	
 Withhold dose until toxicity resolves to Grade 1 or baseline, unless condition fits exceptions noted below. If resolved within 14 days, resume treatment at dose reduced by 25% (first dose reduction), or 50% (second dose reduction). Consider supportive care recommendations. If toxicity is resolved within period longer than 14 days, continuation of treatment may be considered on an individual basis if benefit to subject can be demonstrated and if the investigator and medical monitor agree that for a given subject the benefits may outweigh the risks 
Exceptions:
 
 Subjects who develop G3 toxicities which respond to standard treatment and resolve to ≤G1 within 48 hours may continue treatment at scheduled or reduced dose Permanently discontinue for grade 3 or greater QTc prolongation i.e., QTcF >500 msec or QTcF increase by > 60 msec from baseline Troponin elevations: See Section 3.9.3 for troponin stopping criteria
Grade 4	
 Permanently discontinue study medication 
Exceptions:
 
 G4 thrombocytopenia with no sign of bleeding, if recovered within 14 days. For dose reductions see Section 3.10 G4 lymphopenia (dose reductions by 25-50% may be considered)

a. Possibly related to investigational drug.

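### At the same QTc thresholds, Protocol 3.9.2 has treatment withheld, while Table 13 requires permanent discontinuation if the event is possibly drug-related

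*Protocol*

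**What the plan says.** Section 3.9.2 (QTc Stopping Criteria) sets two triggers, a QTcF above 500 msec or an increase of more than 60 msec from baseline. For either one, "Study treatment will be withheld in a subject who meets the corrected QT (QTc" interval criteria. Its footnote explains the averaging of three ECGs and repeats the action: "use the averaged QTc values of the 3 ECGs to determine whether the subjects should have study treatment withheld". The section gives no duration, recovery criterion or restart route, and it does not say that the stop is permanent.

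Table 13 in Section 3.10.3 lists QTc under the Grade 3 exceptions: "Permanently discontinue for grade 3 or greater QTc prolongation i.e., QTcF >500 msec or QTcF increase by > 60 msec from baseline". The table's footnote a limits it to toxicity "Possibly related to investigational drug". The Grade 3 default in the same cell, from which QTc is excepted, is "Withhold dose until toxicity resolves to Grade 1 or baseline, unless condition fits exceptions noted below". The lead-in to the table reads "For GSK2857916 toxicities not specifically addressed in the protocol follow the guidelines outlined in" Table 13.

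Three other sections bear on the question:

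- Section 6.3 ends treatment on unacceptable toxicity, which includes meeting the stopping criteria in 3.10 or in the other safety management guidelines.
- Section 7.3.4 fixes Fridericia's correction and refers to 3.9.2 for the QTc *withdrawal* criteria.
- Section 3.3.3 lets a Part 1 subject with a dose-limiting toxicity (DLT) remain on study only if, among other conditions, no stopping criterion was met.

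**The concern.** An investigator facing a QTcF above 500 msec that may be drug-related finds two instructions. One uses the protocol's ordinary word for a pause, and the other takes the subject off drug for good. The ECG section directs sites to 3.9.2 and not to Table 13. The lead-in to Table 13 gives a reader some reason to think that a toxicity with its own section, as QTc has, is governed there. A site that stops reading at 3.9.2 could resume dosing once the interval has recovered, and the other rule forbids that.

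What is at stake is re-exposure after a marked QT prolongation in a first-in-human trial. The immediate response is not in doubt, since both texts stop drug at once. Dose-limiting toxicity classification, power and type I error are not touched.

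**Working it through.** No arithmetic applies. The check is a comparison of the texts.

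1. **Same trigger?** Yes. Both places use 500 msec and 60 msec from baseline. The 60 msec bullet in 3.9.2 says QTc where Table 13 says QTcF, but 7.3.4 fixes Fridericia's formula throughout, so the measure is the same.

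2. **Same population?** They overlap. Section 3.9.2 applies whatever the cause, while footnote a confines Table 13 to possibly related toxicity. For a possibly related event both rules apply.

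3. **Same action?** Not as worded. The Grade 3 cell of Table 13 sets a hold until recovery against the QTc exception of permanent discontinuation. Section 3.10.2 draws the same contrast for pneumonitis: Grades 1 and 2 are withheld with retreatment possible on resolution, and Grades 3 and 4 are permanently discontinued. Febrile neutropenia is withheld and may restart. Where a permanent stop is meant nearby, it is stated: for liver events in 3.9.1.1, and in 3.9.3 for troponin above the infarction threshold. By the protocol's own usage, *withheld* reads as temporary.

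4. **Does the heading of 3.9.2 settle it?** Not alone. Sections 3.9.3 and 3.9.4.1 are also headed as stopping criteria and allow restart. For troponin, "Any re-start of study treatment must be discussed with the GSK medical monitor who will consult with a member of the internal cardiotoxicity panel"; for LVEF, "after consultation and approval of the GSK Medical Monitor, the subject may be restarted on GSK2857916 at a reduced dose".

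5. **Do other sections narrow the gap?** Yes, for much of it.
   - *Part 1, Cycle 1.* Table 13 describes these thresholds as Grade 3 or worse. Under 3.3.3, a Grade 3 or greater non-hematologic event in the DLT period (21 days on Schedule 1, 28 days on Schedule 2) whose relationship cannot be ruled out is a DLT, unless one of the listed exceptions applies. QTc prolongation is not listed. Because a criterion headed as a stopping criterion has been met, the subject may not stay on study.
   - *Later cycles in Part 1, and all of Part 2.* Section 3.3.3 does not reach these. The general sentence in 6.3 and the label in 7.3.4 favour a permanent stop, but neither changes the verb in 3.9.2.

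6. **What remains?** Mainly possibly related events after Cycle 1 in Part 1 or at any time in Part 2, handled by a site that reads 3.9.2 alone and takes it as a temporary hold.

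**The case against.** The strongest reply is that the two texts are compatible. Section 3.9.2 gives the immediate step once the averaged ECGs are in, and Table 13 gives the final disposition. A site that withholds and then permanently discontinues complies with both. Section 3.9.2 contains no restart provision, whereas the troponin, LVEF and valve sections spell out theirs and use words such as *interrupt* or *temporarily*. The mandatory sentence in 6.3 covers stopping criteria in the safety management guidelines, and Section 3.9 carries that title. The general lead-in to Table 13 does not displace an express QTc line inside the table. As background on intent only, the Amendment 1 rationale records a regulator's request that subjects with a rise above 60 msec come off study treatment, and a restart paragraph was removed from 3.9.2 at that time.

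Most of this stands. It shows that a permanent stop is the better reading and that no text authorises re-dosing. It does not remove the inconsistency, because the reconciliation works only for a reader who consults Table 13 alongside 3.9.2, and 3.9.2 does not point there.

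Two stronger readings are tempting. A reader might infer that affected subjects could go on to receive most of a full course of treatment, with the 14-day dose-delay rule in 6.3 as the only brake. The documents do not support this. It would require ignoring Table 13, the mandatory sentence in 6.3 and, for Part 1 DLTs, Section 3.3.3. A reader might also infer a second contradiction for events clearly unrelated to drug. There is none: Table 13 does not apply to them, 3.9.2 permits no restart, and the stopping-criteria sentence in 6.3 is not limited to related events. Whether to allow such subjects back is a sponsor choice about unstated detail.

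**Conclusion.** The point holds for possibly drug-related events. Sections 3.9.2 and 3.10.3 name different actions at identical thresholds, and the verb in 3.9.2 is the one that Table 13 reserves for a temporary hold. The wording is wrong as it stands and worth correcting because it concerns cardiac safety, but it leaves the intended outcome recoverable from the rest of the protocol.

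The size is small and cannot be counted, since the document gives no rate of QTc events. The conclusion rests on two readings: that *withheld* carries the same sense in 3.9.2 as elsewhere in the protocol, and that 3.3.3 treats the QTc limits as stopping criteria, as the heading of 3.9.2 indicates.

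**What to change.** In Section 3.9.2 and its footnote, replace *withheld* with wording that treatment is stopped at once when either averaged criterion is met, and is permanently discontinued when the event is possibly related to study drug, as Table 13 has it. Add a cross-reference in each direction between 3.9.2 and Table 13. While the text is open, the sponsor may also state the action for clearly unrelated events and write QTcF in the 60 msec bullet. Both are optional clarifications.

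The cost is a wording amendment, with no change to design, sample size or analysis. The clinical downside is that a subject with a transient, possibly related rise cannot resume treatment, but Table 13 already imposes that.
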